3.3 STUDY DRUG ADMINISTRATION AND EXTENT OF EXPOSURE

Subjects will be treated with somavaratan or daily rhGH treatment for 12 months and may then elect to enroll in the long-term open-label safety study (Protocol 13VR3) and continue or start somavaratan treatment.

The selected somavaratan dose, which was chosen using results obtained from other protocols, is 3.5 mg/kg administered twice-monthly. The selected daily rhGH dose is 34

$\mu\text{g/kg}$, the highest dose approved for GHD children in all regions where this study will be conducted.

3.4 STUDY POPULATION

The study population will consist of naïve to treatment, pre-pubertal children with growth hormone deficiency (GHD). A 3:1 randomization ratio will be used for the somavaratan dosing arm and the daily rhGH dosing arm, respectively. Screening and randomizations will continue until a minimum of approximately 84 subjects have been enrolled or enrollment has been completed based on the sample size re-estimation procedure.

3.5 SAMPLE SIZE CALCULATION/JUSTIFICATION

Sample size estimates are derived from considerations for non-inferiority testing of twice monthly somavaratan versus daily rhGH. The somavaratan arm will be tested against daily rhGH using a one-sided test procedure. Assuming a 3:1 somavaratan to daily rhGH subject ratio, a standard deviation of ≤ 3.0 cm/yr in annual height velocity, an alpha of 0.05 (one-tailed 0.025) and a non-inferiority limit for difference in mean height velocity of 2.0 cm/yr, a total of 76 subjects are required: 57 for the somavaratan dosing arm and 19 for the daily rhGH arm. The total number of planned subjects is 84 (76 plus 8 for potential drop-outs). An independent statistical consulting group will conduct sample size re-estimation using the observed variance in height velocity to determine if *a priori* assumptions were valid and notify Versartis, Inc. if the total sample size should be increased to ensure statistical analyses with adequate power. Assuming the SD (standard deviation) is not greater than 3.5, the sample size should be no greater than 136 subjects.

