Sample size estimates are derived from considerations for non-inferiority testing of twice-monthly somavaratan versus daily rhGH. The somavaratan arm will be tested against daily rhGH using a one-sided test procedure. Assuming a 3:1 somavaratan to daily rhGH subject ratio, a standard deviation of ≤ 3.0 cm/yr in annual height velocity, an alpha of 0.05 and a non-inferiority limit for difference in mean height velocity of 2.0 cm/yr, a total of 76 subjects are required: 57 for the somavaratan dosing arm and 19 for the daily rhGH arm. The total number of planned subjects is 84 (76 plus 8 for potential drop-outs). An independent statistical consulting group will conduct sample size re-estimation using the observed variance in height velocity to determine if *a priori* assumptions were valid and notify the Sponsor if the total sample size should be increased to ensure statistical analyses with adequate power.

TABLE OF CONTENTS

APPROVAL/SIGNATURE PAGE: SPONSOR AND CONTRACT RESEARCH ORGANIZATION	2
SUMMARY OF CHANGES IN VERSION 4	3
SYNOPSIS: PROTOCOL 14VR4	4
LIST OF ABBREVIATIONS AND DEFINITIONS OF TERMS	16
1 INTRODUCTION	19
1.1 Clinical Experience	20
1.1.1 Adult Growth Hormone Deficiency	20
1.1.2 Pediatric Growth Hormone Deficiency	21
1.1.2.1 Protocol 12VR2	21
1.1.2.2 Protocol 13VR3	21
1.1.2.3 Protocol J14VR5	22
1.1.3 Summary of Clinical Experience	22
2 STUDY OBJECTIVES	24
2.1 Primary Objective	24
2.2 Secondary Objective	24
3 INVESTIGATIONAL PLAN	25
3.1 Overall Study Design and Plan	25
3.2 Rationale for Study Design and Control Group	25
3.3 Rationale for Dose Selection	25
3.4 Study Duration and Dates	26
3.5 Safety Reviews and Stopping Rules	26
3.5.1 Data and Safety Monitoring Board Membership	26
3.5.2 Stopping Rules	26
3.5.2.1 Individual Subjects	26
3.5.2.2 Somavaratan Treatment Cohort	27
4 STUDY POPULATION SELECTION	28
4.1 Study Population	28
4.2 Inclusion Criteria	28
4.3 Exclusion Criteria	29
4.4 Subject Withdrawals and Replacements	30
5 STUDY TREATMENT(S)	31
5.1 Description of Treatment(s)	31
5.1.1 Somavaratan Treatment Cohort	31
5.1.2 Recombinant Human Growth Hormone Treatment Cohort	31
5.2 Treatments Administered	31
5.3 Selection and Timing of Dose for Each Subject	32

5.4	Method of Assigning Subjects to Treatment Groups and Subject Number Assignments	32
5.5	Concomitant Therapy	32
5.6	Restrictions	33
5.7	Treatment Compliance	33
5.8	Packaging and Labeling	33
5.8.1	Somavaratan	33
5.8.1.1	Assembly and Labeling of Unit Doses	34

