9.2 Determination of Sample Size

Between 84 and 136 subjects are expected to complete the study. Sample size estimates are derived from considerations for non-inferiority testing of twice-monthly somavaratan versus daily rhGH. The somavaratan treatment cohort will be tested against the daily rhGH treatment cohort using a one-sided test procedure. Assuming a 3:1 somavaratan to daily rhGH subject ratio for each comparison, a standard deviation of ≤ 3.0 cm/yr. in annual height velocity, an alpha of 0.05 and a non-inferiority limit for difference in mean height velocity of 2.0 cm/yr., a total of 76 subjects are required: 57 for the somavaratan treatment cohort and 19 for the daily rhGH treatment cohort. The total number of planned subjects is 84 (76 plus 8 for potential drop-outs).

A non-inferiority margin of -2.0 cm/yr is chosen for analysis of the primary endpoint. This margin was used for the approval of Valtropin®. The margin is considered conservative when compared to the distribution of first year height velocities for children with similar degrees of GHD and treated with daily rhGH in a dose similar to the daily rhGH treatment cohort of this study. For children with moderate (“less severe”) GHD, ages 4 to 10, the differences between the 3rd and 50th percentile for the first year height velocity is approximately 3–4.5 cm/yr.

An independent statistical consulting group will conduct sample size re-estimation using the observed variance in height velocity to determine if *a priori* assumptions were valid and notify the Sponsor if the total sample size should be increased to ensure statistical analyses with adequate power. If the assumption of variance in height velocity has been underestimated as determined in the sample size re-estimation procedure, the sample size may be increased up to 136 subjects.

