1. INTRODUCTION/BACKGROUND

This statistical analysis plan (SAP) describes the data analysis specifications for Protocol 14VR4 entitled “Comparison of Somavaratan (VRS-317), a Long-acting Human Growth Hormone, to Daily rhGH in a Phase 3, Randomized, One-year, Open-label, Multi-center, Non-inferiority Trial in Pre-pubertal Children with Growth Hormone Deficiency,” Version 4, 5 April 2017.

This SAP follows the International Conference on Harmonisation (ICH) Guidelines E3 and E9. All statistical analyses will be performed using SAS[®], Version 9.4 or higher. In cases in which the analyses in this SAP differ from those in the study protocol, the analyses in the SAP supersede those in the protocol. Should differences exist, these will be described in Section 6.2 of this document.

This protocol is a randomized, multi-center, open-label, non-inferiority study for pre-pubertal naïve to treatment children with growth hormone deficiency (GHD). Subjects will be randomized to receive 3.5 mg/kg somavaratan twice-monthly or daily treatment with rhGH. Safety and efficacy of these treatments over the course of one year will be evaluated along with changes in pharmacodynamic responses (IGF-I, IGF binding protein-3 (IGFBP-3), growth hormone binding protein (GHBP) and acid labile subunit (ALS)), bone age, weight, body mass index (BMI), height standard deviation scores (HT-SDS), and anti-drug antibody (ADA) responses.

Somavaratan is a fusion protein consisting of recombinant human growth hormone (rhGH) and two sequences (XTEN) of hydrophilic amino acids, designed to maintain active drug levels for a longer period of time than currently available therapies. It is being developed for treatment of GHD in adults and children and as a long-acting alternative to daily rhGH injections, which is currently the only approved treatment in the United States for adults and children with growth hormone deficiency.

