6.2 CHANGES FROM PROTOCOL SPECIFIED ANALYSES

Changes to the protocol may result in changes to the planned analyses, and may change the defined analysis endpoints and methods. Any changes to analysis as a result of changes to the protocol will be documented as an amendment to this SAP. Other than transformations or modeling needed to address the structure and distribution of the resulting data, additional analyses will be for exploratory purposes only.

The changes from the protocol specified analyses are:

1. Growth Hormone Binding Protein (GHBP) and Acid Labile Subunits (ALS) will be summarized but not analyzed as secondary endpoints.
2. Inclusion of Levine's test for homogeneity of variance
3. Inclusion of Welch's t-test if there is unequal variance
4. Replaced multiple imputation for missing data with tipping point analysis

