6.3 STUDY HYPOTHESES

The primary comparison of the annualized height velocity between somavaratan and daily rhGH is based on the null hypothesis that the difference is less than or equal to -2.0 cm/yr, the non-inferiority margin.

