6.11.1 Primary Efficacy Endpoint

Annual height velocity will be calculated using the formula below:

$$\begin{aligned} \text{Height Velocity} \left(\frac{\text{cm}}{\text{year}} \right) \\ = \left[\frac{\text{Month X Height (cm)} - \text{Baseline Height (cm)}}{\text{Month X date} - \text{Baseline date}} \right] * 365.25 \end{aligned}$$

The primary analysis will be the comparison of the annual height velocity between somavaratan and daily rhGH, with null hypothesis that the difference is less than or equal to -2 cm/year, the non-inferiority margin. An Analysis of Covariance (ANCOVA) model will be used to determine the adjusted (least squares) means and SE to determine the confidence interval (CI) of the difference. The model fixed effects are treatment group, region and gender, with baseline age, baseline IGF-I SDS, and baseline height as covariates. The ANCOVA is used to adjust for the influence of these covariates, and not to determine if these covariates themselves are statistically significant factors. A reduced model removing covariates with $p > 0.10$ may also be considered for exploratory purposes. The randomization stratification should result in balance between the two treatments in terms of the factors. Levene's will be used to determine if the variances is equal between the two treatment groups. If there is evidence of unequal variance, a Welch test on the treatment main effects will be performed with null hypothesis of somavaratan HV - daily rGH HV ≤ -2 cm. Rejection of this null hypothesis will be evidence of non-inferiority of somavaratan to daily rGH.

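### The SAP gives one-tailed 0.025 for the primary test but keeps the 76 subjects that fit the protocol's one-sided 0.05, and no level is stated where the test is defined

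*SAP*

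**What the plan says.** Protocol 9.2 fixes the sidedness: "The somavaratan treatment cohort will be tested against the daily rhGH treatment cohort using a one-sided test procedure". The synopsis gives the level and the size: "an alpha of 0.05 and a non-inferiority limit for difference in mean height velocity of 2.0 cm/yr, a total of 76 subjects are required". Protocol 9.2 uses the same inputs, an SD of at most 3.0 cm/yr and 3:1 allocation, and reaches the same 57 somavaratan and 19 daily rhGH subjects, with 84 planned after 8 are added for drop-outs.

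SAP 3.5 also describes a one-sided test and repeats the SD, margin, ratio, 57/19 split and 84. Its level is different: "an alpha of 0.05 (one-tailed 0.025) and a non-inferiority limit for difference in mean height velocity of 2.0 cm/yr, a total of 76 subjects". It adds a ceiling of 136 subjects if the SD is not above 3.5.

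SAP 1 says that "the analyses in the SAP supersede those in the protocol", and promises: "Should differences exist, these will be described in Section 6.2 of this document". SAP 6.2 opens its list with "The changes from the protocol specified analyses are" and gives four items: GHBP and ALS, the homogeneity test, the Welch test and the tipping-point analysis. Alpha is not among them.

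SAP 6.3 states "the null hypothesis that the difference is less than or equal to -2.0 cm/yr, the non-inferiority margin". SAP 6.11.1 uses the ANCOVA "means and SE to determine the confidence interval (CI) of the difference", with a Welch test if variances are unequal. Neither section gives an alpha or a confidence level, nor do SAP 5.1, SAP 5.3 or protocol 9.1. The only level for a treatment comparison in SAP section 6 is p < 0.05, for the secondary endpoints (6.11.2). The 0.10 thresholds in 5.3 and 6.11.1 concern covariates only.

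**The concern.** The two documents give different levels for the same one-sided test and the same required number. Halving a one-sided alpha with everything else fixed must raise the sample size or lower the power, so 76 cannot serve both at a common power target.

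Two things are at stake. The first is the decision rule of a pivotal, open-label trial. Whether the lower limit of a two-sided 90% or 95% interval decides non-inferiority has to be inferred from a sentence about sample size, while the protocol still reads as one-sided 0.05. The second is power. The re-estimation is asked only for adequate or appropriate power, with no number. Protocol 9.2 provides for an increase if the variance was underestimated. If the SD turns out to be 3.0 as assumed, the trial may stay near 84 subjects at a level for which that number was not derived.

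**Working it through.** **Inputs from the documents.** Margin 2.0 cm/yr, SD 3.0 cm/yr, 3:1 allocation, 57/19 required, 84 planned (63/21 at 3:1), maximum 136 (102/34). **Assumptions, because neither document gives them:** true difference 0, no variance reduction from covariates, and 80% as the reference power.

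**Formulas.** SE = SD × √(1/n_s + 1/n_c). Power (normal) = Φ(2/SE − z₁₋α). Control-arm size = (4/3) × [SD × (z₁₋α + z_power)/2]², rounded up; the total is four times that. The noncentral-t version uses n_s + n_c − 2 degrees of freedom.

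**Reproducing the 76.** At one-sided 0.05 and 80% power: (4/3) × [3 × (1.645 + 0.842)/2]² ≈ 18.55, so 19 control, 57 somavaratan, total 76. The t version also gives 76. The protocol's number is therefore reproduced exactly.

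**Same inputs at one-sided 0.025.** (4/3) × [3 × (1.960 + 0.842)/2]² ≈ 23.55, so 24 + 72 = 96 (normal). The t version gives 25 + 75 = 100; 96 just misses, at 79.9%. With the plan's drop-out share of 8/84, that is 107 to 111 enrolled.

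**Power at the plan's sizes.** For 57/19, SE = 3 × √(1/57 + 1/19) = 0.795 and 2/0.795 = 2.517. At 0.05, Φ(2.517 − 1.645) = 0.808; at 0.025, Φ(2.517 − 1.960) = 0.711.

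| Analysed | SD | One-sided 0.05 (t / normal) | One-sided 0.025 (t / normal) |
|---|---|---|---|
| 76 (57/19) | 3.0 | 80.2% / 80.8% | 70.0% / 71.1% |
| 84 (63/21) | 3.0 | 83.6% / 84.2% | 74.4% / 75.4% |
| 136 (102/34) | 3.0 | 95.6% / 95.7% | 91.7% / 92.0% |
| 136 (102/34) | 3.5 | 89.0% / 89.3% | 81.7% / 82.3% |

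**Range over the unstated inputs, at one-sided 0.025 and SD 3.0.**
- Power target 70%: 76 (normal) or 80 (t). Power target 90%: 128 or 132.
- True difference −0.25 cm/yr: 59–60% with 76, 63–64% with 84.
- True difference +0.25 cm/yr: 80–81% with 76, 84% with 84 (83.7% t, 84.5% normal).
- Covariate adjustment: 80% needs a residual SD of 2.66–2.69 with 76 (R² about 0.19–0.21), or 2.80–2.83 with 84 (R² about 0.11–0.13). No R² is given.

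**The 136 ceiling.** At SD 3.5 and 80% power, one-sided 0.025 needs 132 and one-sided 0.05 needs 104. At 80% power, then, 76 and 136 in the same SAP paragraph appear to rest on different alphas. This does not settle the matter alone, because one-sided 0.05 at 90% power needs 140 (normal) or 144 (t).

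**Effect on the decision.** With 63/21 and SD 3.0, SE = 0.756 with 82 degrees of freedom. Non-inferiority is met if the observed difference exceeds −2 + 1.664 × 0.756 = −0.74 at 0.05, or −2 + 1.989 × 0.756 = −0.50 at 0.025. Results between these limits change verdict with the level. With 102/34 the band is −1.02 to −0.82.

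**The case against.** The SAP governs, and it gives one-tailed 0.025. A reader who follows it arrives at a two-sided 95% interval, and Type I error is then 2.5%. The SAP wording may be meant only as a clarification that two-sided 0.05 equals one-sided 0.025. No target power is stated, and by the normal formula 76 does meet 70% at 0.025, so the mismatch in size is an inference. The primary analysis uses all randomized subjects, so 84 is a fairer number than 76. Age and IGF-I SDS are described in protocol 3.2 as affecting height velocity, so the ANCOVA could recover the missing power. Re-estimation can raise the total to 136.

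Much of this stands. There is no inflation of Type I error if the SAP is followed, and the power shortfall is bounded and depends on assumptions. It does not remove the point. If 0.025 was always meant, the 76 does not reach 80% power on its own inputs; if 0.05 was meant, the SAP is wrong. One document needs correcting either way. The covariate gain is not quantified in the plan, and re-estimation responds to variance, so it need not act when the SD is 3.0. Enrolling 136 would ease the power problem but would still leave the protocol and SAP with different levels, and no level where the test is specified.

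**Conclusion.** The concern holds and must be fixed. The size carried into the SAP fits one-sided 0.05 at 80% power, not the governing 0.025. The change of level is not listed where the SAP says it will be, and the primary analysis sections give no level for either the ANCOVA or the Welch fallback.

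With a true difference of 0, SD 3.0 and no covariate adjustment, the cost at 0.025 is about 10 percentage points of power with 76 analysed (80–81% down to 70–71%) and about 9 with 84 (84% down to 74–75%). Under the SAP this is a risk of a failed trial at the minimum size, not of a false claim. The effect of the SAP's zero-growth imputation on variance and bias is not quantified here and could change these figures.

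**What to change.** - State one rule: one-sided 0.025, with non-inferiority concluded if the lower limit of the two-sided 95% interval for the least-squares mean difference lies above −2.0 cm/yr. Put it in the protocol synopsis, protocol 9.2 and SAP 3.5, 6.3 and 6.11.1, with the same level for the Welch fallback.
- List the change of alpha in SAP 6.2.
- State the target power and the assumed true difference.
- Restate the size in SAP 3.5 and protocol 9.2. At SD 3.0 and true difference 0, 76 evaluable subjects give about 70% and 84 about 75%; 80% needs about 96 to 100; 136 give about 92%, or 82% at SD 3.5.
- Run the variance-based re-estimation to the stated power at one-sided 0.025, within the existing maximum of 136.

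The cost is wording in those sections and a less favourable stated power at 76 and 84. If the target is 80% and the assumptions hold, enrolment would need to exceed 84 but not the existing cap.

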3.6 RANDOMIZATION SCHEME

The randomization will be stratified by region (North America and Europe), age (above and below anticipated median age of 7.5 years) and baseline IGF-I SDS (above and below anticipated median of -1.7) in a 3:1 ratio of either VRS-317 or daily rhGH treatment, respectively.

4. ANALYSIS SETS

4.1 PRIMARY ANALYSIS POPULATION AND MODIFIED INTENT TO TREAT (mITT)

The primary analysis population (ITT, Intent-To-Treat) will be based on all randomized subjects. In addition, a mITT population, defined as all subjects completing at least one month of dosing with completed efficacy assessments at the Month 1 visit will also be created. Subjects completing less than one month of treatment or without a post-treatment height measurement will not be included in the mITT population. Based on previous studies with somavaratan, the expectation is that very few subjects who randomize will not be able to complete at least 1 month of treatment and evaluations.

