4.4 Subject Withdrawals and Replacements

Consent may be withdrawn at any time for any reason by subject or subject caregiver without prejudice to future treatment. The investigators or medical monitor may withdraw a subject if it is judged to be in the best interest of the subject or if it is clear the subject cannot comply with the protocol. For early withdrawals, the tests and evaluations listed for the Month 12 visit should be completed, if possible.

Subjects that develop a new significant medical condition at any point during the trial may be withdrawn.

To achieve the planned sample size for analysis, additional subjects will be enrolled as needed to account for subjects who withdraw prior to completing one month of treatment and Month 1 height evaluations.

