9.3 Analysis Populations

9.3.1 *Safety Population*

The safety population will consist of all subjects completing a screening evaluation and receiving any amount of study drug.

9.3.2 *PK/PD Population*

The PK/PD analysis population will consist of all subjects receiving study drug and having at least one post-treatment PK/PD assessment. A PK/PD per protocol subset will include all subjects with complete PK/PD assessments and no missed doses in the dosing interval prior to a PK/PD assessment.

9.3.3 *Intent-to-Treat Population*

The intention to treat analysis (ITT) will be the primary analysis population. The ITT population will consist of all subjects completing at least one month of dosing with completed efficacy assessments at the Month 1 Visit. For subjects completing less than the 12 months of treatment, the height velocity at 12 months will be imputed from the change from baseline of last measurement of HT-SDS. With this procedure, a 12 month height velocity measurement will be available for all subjects in the ITT.

Baseline characteristics of the excluded subjects will be reported. In the event that numerous imputations are required, comparisons of subject that completed versus those who dropped and required imputation will be done.

9.3.4 *Per Protocol Population*

A per protocol analysis will be used to evaluate efficacy parameters. All subjects completing one year of continuous study dosing with efficacy assessments at Month 12 will be included. Patients with major dosing deviations ($\geq 10\%$ of total assigned doses missed) will be excluded from per protocol analysis. Missing data for the per protocol population will not be imputed.

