6.4 HANDLING OF MISSING VALUES AND OUTLIERS

Because of subject privacy limitations, birth dates may only be reported by month and year in certain locations. Where the specific birth day is not available, the day of month will be imputed as the 15th.

For the primary endpoint in the ITT population, missing height at 12 months will be imputed from the last available height. This imputation assumes no growth after the last available measurement observed at study exit. This is an extremely conservative approach. For example, a █ year old █ subject who discontinued at month 6 with annualized HV of 6 cm/yr (Day 1 height of █ cm and Month 6 height of █) will have the height at 12 months imputed to █ cm, resulting in an annual HV of 3 cm/yr.

For the sensitivity analysis of the effect of missing data on the primary endpoint, height velocity at Month 12, a tipping point approach will be used. The missing data will be imputed as follows:

For the control group:

1. All subjects to the control group mean (calculated without subjects missing endpoint)
2. 50% to the group mean, 50% to the HV associated with each subjects last reported height (no additional gain in height)
3. Each subject's HV imputed based on its own last reported height

For the somavaratan group:

1. All subjects to the somavaratan group mean (calculated without subjects missing endpoint)
2. 50% to the group mean, 50% to the HV associated with each subjects last reported height (no additional gain in height)
3. Each subject's HV based on its own last reported height
4. Each subject imputed to HV based on last reported height, minus 1 cm.
5. Each subject imputed to HV based on last reported height, minus 2 cm (the non-inferiority margin, to avoid imputing to a common mean).

The reduction of the imputed HV by -1 and -2 cm will be limited to a minimum 0 HV, as negative HV is not possible. This will result in a total of 15 comparisons which should cover the range of plausible results for the subjects who are not able to provide Month 12 height velocity, and accounts for combinations where the somavaratan drop outs will have worse outcomes than drop outs in the control group (e.g., control group imputation 1 versus somavaratan imputations 2 to 5).

No imputations will be considered for the PP populations.

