6.11 EFFICACY ANALYSES

The primary efficacy analyses will be done using the All Randomized population, and will also be done using the mITT and PP populations.

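### The SAP changes the primary analysis set and the primary imputation without declaring either, and its no-further-growth rule gives zero height velocity to a child with no post-baseline height, which in the daily rhGH arm favours non-inferiority.

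*SAP*

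**What the plan says.** **Analysis set.** Protocol 9.3.3: "The ITT population will consist of all subjects completing at least one month of dosing with completed efficacy assessments at the Month 1 Visit". SAP 4.1: "The primary analysis population (ITT, Intent-To-Treat) will be based on all randomized subjects". The SAP keeps the protocol's set under the name mITT. SAP 6.11 confirms the order: "The primary efficacy analyses will be done using the All Randomized population, and will also be done using the mITT and PP populations".

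**Imputation.** Protocol 9.1 fills a missing 12-month height from the child's last height SDS, so the child keeps growing at the rate expected for age. It then takes 2 cm/yr off imputed somavaratan values, to avoid imputing both arms to a common mean. SAP 6.4 says for the primary endpoint: "missing height at 12 months will be imputed from the last available height". It assumes no growth after that measurement and describes this as a very conservative approach. The 2 cm/yr reduction survives only as one somavaratan scenario in the tipping-point analysis.

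**Declaration.** SAP 1 says the SAP overrides the protocol and adds: "Should differences exist, these will be described in Section 6.2 of this document". SAP 6.2 introduces its list with "The changes from the protocol specified analyses are" and gives four items: GHBP and ALS summarised only, a homogeneity-of-variance test, Welch's test, and tipping point in place of multiple imputation. Neither the set nor the primary single imputation is listed.

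**The concern.** The protocol's set guaranteed every child a Month 1 height, so the imputation always had a post-baseline value to start from. All randomised removes that guarantee, and SAP 6.4 has no separate rule for a child with only a baseline height. Taken literally, the imputed Month 12 height equals baseline and the annual height velocity (HV) is 0. This is an inference from the rule; the SAP does not state it.

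Such children are possible. Under Protocol 5.4 the assignment is disclosed after randomisation, and under 7.2.1 the Day 1 procedures follow randomisation, so a family can withdraw knowing the arm.

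A no-growth rule is conservative only for the somavaratan arm. In the control arm it lowers the comparator mean and moves the result towards non-inferiority. With about 21 rhGH children, one zero carries real weight in the primary test.

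**Working it through.** **1. The rule, on the SAP's own example.** A child leaves at Month 6 with an annualised HV of 6 cm/yr. Growth so far is 6 × 0.5 = 3 cm and none is added, so annual HV is 3 cm/yr, as SAP 6.4 states. With only a baseline height H0, the same rule gives (H0 − H0)/365.25 × 365.25 = 0.

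**2. Inputs.** Margin 2.0 cm/yr, SD 3.0, one-tailed alpha 0.025 (SAP 3.5). N=84 at 3:1 is 63 somavaratan and 21 rhGH. The maximum of 136 is 102 and 34 (Protocol 4.1); SAP 3.5 links it to an SD up to 3.5. The rhGH mean is taken as 10 cm/yr, within the 9.5–11 of Protocol 1.

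The planned 76 reproduces only at one-sided 0.05, with 80% power assumed (none is stated). The rhGH number is (1.645 + 0.842)² × 3² × (1 + 1/3)/2² = 18.6, so 19, and 3 × 19 = 57. At one-tailed 0.025 it is (1.960 + 0.842)² × 3 = 23.5, so 24 + 72 = 96. That is a separate question; the SAP's 0.025 is used below.

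**3. Shift in the mean.** One rhGH zero lowers that mean by 10/21 = 0.48 cm/yr (9.5/21 = 0.45 to 11/21 = 0.52), about a quarter of the margin. At 34 rhGH children it is 10/34 = 0.29. At the null boundary the somavaratan mean is 8, so one somavaratan zero lowers it by 8/63 = 0.13.

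**4. False non-inferiority rate.** Simulated at a true difference of −2.0, with the stated children fixed at the stated HV and the rest normal. At least 100,000 trials per case; ranges are between runs.

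| Children fixed | N (somavaratan/rhGH), SD | Pooled t | Welch |
|---|---|---|---|
| None | 63/21, 3.0 | 2.5% | 2.5% |
| One rhGH at 0 | 63/21, 3.0 | 7.2–7.3% | 4.7–4.9% |
| Two rhGH at 0 | 63/21, 3.0 | 17–18% | about 9% |
| One somavaratan at 0 | 63/21, 3.0 | 1.3–1.4% | 1.6% |
| One in each arm at 0 | 63/21, 3.0 | 4.2–4.4% | 3.2% |
| One rhGH, two somavaratan at 0 | 63/21, 3.0 | 2.5% | 2.0% |
| One rhGH, three somavaratan at 0 | 63/21, 3.0 | 1.4% | 1.3% |
| One rhGH at 0 | 102/34, 3.0 | 6.1% | 4.6% |
| One rhGH at 0 | 102/34, 3.5 | 5.5–5.6% | 4.6% |
| One rhGH leaving at Month 1, HV 10/12 = 0.83 | 63/21, 3.0 | 6.6–6.7% | 4.7% |

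For one rhGH zero at 63/21, the range over rhGH means of 9.5 to 11 is 6.9–7.7%. ANCOVA with region, gender and three covariates gives 6.9–7.9% (6.1–6.8% at 102/34, SD 3.0; 20,000 trials). Using Welch only when Levene's test signals unequal variance gives 7.0%.

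**5. How likely is the bad case?** Under 3:1 allocation a single exit falls in the rhGH arm one time in four: 0.25 × 7.22% + 0.75 × 1.33% = 2.8%. With equal exit probabilities at 63/21, the pooled t-test gives 2.8% at 1%, 3.0% at 2% and 3.7% at 5% exits. With 5% exits on rhGH and 1% on somavaratan (an assumption), it gives 8.7%.

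**6. Set or rule?** Leaving the child out, as the protocol's set does, returns the error to 2.5%. But an rhGH child who leaves just after Month 1 is inside the protocol's set and the mITT, and under the SAP's rule gives 6.6–6.7%. Most of the distortion therefore comes from the no-growth rule.

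**The case against.** Several stronger readings are tempting and the documents do not support them.

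- A reader might infer that the plan roughly triples the error. That needs an rhGH zero with no somavaratan zero, at N near 84, with the pooled or ANCOVA test. Nothing in the documents shows more early exits in the daily arm, and exclusion criterion 18 screens out families unwilling to accept their assignment. SAP 4.1 expects very few such children. Protocol 4.4 and 7.3 also ask early leavers to complete the Month 12 evaluations, which include height.
- A reader might blame the all-randomised set. Step 6 shows otherwise, and that set is the better primary choice.
- A reader might see a contradiction in the mITT definition, because SAP 4.1 adds "Subjects completing less than one month of treatment or without a post-treatment height measurement will not be included in the mITT population". That sentence lists exclusions and admits nobody. A completer who missed Month 1 simply fails the first condition, so both sentences can hold.
- A reader might think replaced children are left open, because Protocol 4.4 says "additional subjects will be enrolled as needed to account for subjects who withdraw prior to completing one month of treatment". All randomised already keeps them in.

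The planned mITT and PP analyses and the 15 tipping-point combinations, which include control leavers at the control mean, would expose the effect. This stands as mitigation, but none of them is the primary test. If the mITT analysis uses the same imputation, it still contains those who leave soon after Month 1.

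**Conclusion.** Two changes to the primary analysis, the set and the imputation, are missing from the section where the SAP promises to declare them. Read literally, the new rule gives zero growth to a child without a post-baseline height and almost none to an early leaver. In the control arm that is anti-conservative, contrary to the SAP's description.

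The size depends on where the exits fall. With one rhGH zero and no somavaratan zero, the error is about 7% against 2.5% at N=84, about 5.5–6% at N=136, and about 5% with Welch. A somavaratan zero makes non-inferiority harder to show. Averaged over random placement or equal exit rates, the excess is small: 2.8–3.7% at N=84. These figures assume normal HV, an rhGH mean near 10 and one-tailed 0.025.

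This should be corrected before data are seen, because the rule biases the primary test in one arm and a cheap alternative exists. It does not show that the trial will have an inflated error.

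**What to change.** 1. Keep all randomised as the primary set. List in SAP 6.2 both the change of set and the change of primary imputation.
2. In SAP 6.4, do not assign zero growth to a child with no post-baseline height. Impute HV by multiple imputation from observed rhGH children, given age, gender, region, IGF-I SDS and baseline height. Subtract 2.0 cm/yr for somavaratan children, carrying over the size and purpose of the reduction in Protocol 9.1. In a simplified simulation without covariates, this gave an error of 2.4% with one such rhGH child, 2.5% with two, and 2.0–2.3% with such children in both arms.
3. Reconcile the primary imputation for other early leavers with Protocol 9.1, so that control children are not imputed to no growth. Without this, the distortion remains for anyone leaving soon after Month 1.

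The cost is a few SAP sentences and one small imputation step for what should be few children. The main weakness is that the imputation model would be fitted to only about 20 rhGH children, so its covariates should be fixed in advance.
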